8.0 Communication Plan

- Include plan for ensuring all required local site approvals are obtained and notifying the Director of any facility where the research is being conducted but the facility is not engaged.
- Include plan for keeping all engaged sites informed of changes to the protocol, informed consent, and HIPAA authorization
- Include plan for informing local sites of any Serious Adverse Events, Unanticipated Problems, or interim results that may impact conduct of the study.
- Include plan for ensuring the study is conducted according to the IRB-approved protocol.
- Include plan for notifying all local facility directors and LSIs when a multi-site study reaches the point that it no longer requires engagement of the local facility (e.g., all subsequent follow-up of subjects will be performed by the PI from another facility).

Plan for engaged facilities:

- Upon approval of the PI/SC application Form 108, each local site will submit VA Central IRB Form 104 (Local Site Investigator Application), which must be signed by the Local Site Investigator, his/her supervisor, and the local site ACOS/R&D or Chief of Staff.

- Upon VA Central IRB approval of the Form 104 Local Site Investigator Application, the local site R&D Committee must provide written approval for the research to be conducted at the local site before the research begins.
- The Project Coordinator will maintain copies of the local site R&D Committee approvals in the main site regulatory binder.
- Local site Investigators or their designated study team member Research Assistants (RAs) will maintain copies of the main site approval, as well as the local site R&D Committee approvals in their respective local site regulatory binders

Plan for non-engaged facilities:

This research study will not take place at any facility not engaged in the research (i.e., without a Local Site Investigator Project Application approval).

Plan for notifying and obtaining local site approval of amendments and other administrative changes:

- Upon VA Central IRB approval of all PI/SC Amendments and Local Site Amendments (including modifications to the protocol, the procedures for verbal informed consent and HIPAA authorization, and any administrative change approvals), the Project Coordinator will send an electronic copy of the approval and all attachments via email to the Local Site Investigator to submit to the local site R&D Committee for approval (when required by the local site RDC).
- The Project Coordinator will maintain copies of all approval documents, including local site R&D Committee approvals (when required by the local RDC) in the main site study binder.
- The local site Investigator or local site RA will maintain copies of all PI/SC Amendments and Local Site Amendments (including modifications to the protocol, the procedures for verbal informed consent and HIPAA authorization, and any administrative change approvals) that pertain to their respective site in the local site regulatory study binders.
- The local site Investigator or local site RA will maintain copies of their respective local site R&D Committee approvals (when required by the local site RDC) in their local site study binder.
- When the local site R&D Committee requires approval of amendments and/or administrative changes, no change will be implemented prior to receiving documentation of the approval of the local site R&D Committee.

Plan for keeping all engaged sites informed of changes to the protocol, informed consent, and HIPAA authorization:

- A. Regular meetings and conference calls: The Co-PIs will lead regular conference calls and meetings that will include discussions of changes to the protocol, informed consent process and the HIPAA authorization. Study team members will be notified through

these conference calls and meetings of upcoming changes, as well as when the PI receives notification from the VA Central IRB of final approval of such changes.

- The PI will lead weekly meetings to discuss the study status with the study leadership team (select co-Investigators, Project Coordinator, and other study team members)
- The PI will lead weekly conference call discussions with the Local Site Investigator and her study team.
- The PI will lead monthly meetings in person and via conference calls to provide status update/discussions with all Co-Investigators, Local Site Investigator, and all local site study team members

B. **Shared drive:** The Project Coordinator will maintain a shared drive on the Houston VA HSR&D IQuEST secure server (that resides behind the VA firewall) that is accessible to local site study team members. The Project Coordinator will maintain the most current version of all IRB approved documents on this shared drive.

- When new or revised documents are submitted for approval, the Project Coordinator will notify the Local Site Investigator and her study team that changes have been submitted for approval and are under review by the VA Central IRB.
- Upon VA Central IRB approval of a new or revised form, the Project Coordinator will notify the Local Site Investigator and her study team that the new form has been approved. The PI or the Project Coordinator will provide training on newly approved procedures to all local site study team members.
- All local site personnel will be asked to do the following:
 - File a printed copy of the VA Central IRB approval, and all newly approved documents, in the local site study binder.
 - Destroy all blank supply copies of previously approved versions of any newly approved study forms.
 - Begin using the new form, or applying the newly approved procedure, immediately.

Plan for informing local sites of any Serious Adverse Events, Unanticipated Problems, or interim results that may impact conduct of the study:

- The Project Coordinator will notify all participating sites immediately of any SAEs, Unanticipated problems, or interim results that have the potential to affect implementation of the study. A copy of the SAE report or Protocol Deviation report that is submitted to the VA Central IRB will be sent to the Local Site Investigator, as well as their local site study team members via encrypted email. Additional copies will be sent to the local site R&D Committees.
- The PI will discuss SAEs, Unanticipated Problems, Protocol Deviations, and interim results that may affect the conduct of the study during the weekly and monthly, meetings.

Plan for ensuring the study is conducted according to the IRB-approved protocol:

- The importance of conducting the study according to the IRB-approved protocol is emphasized by the PI to all study team members on a regular basis. In particular, all research team members are required to read the IRB-approved protocol (and any subsequent amendments), and research staff will receive specific training from the PI or Project Coordinator regarding protocol elements relevant to their study role before their involvement in the study begins. This study-specific training is over and above the mandatory trainings that all research staff receives.
- During weekly and monthly meetings, the PI will follow-up with the LSI to ensure that she continues to adhere to the protocol and to standard research compliance procedures as required by the VA.
- The PI will require the LSI to hold weekly or bi-weekly meetings with their respective local site study teams.

Plan for notifying all local facility directors and LSIs when a multi-site study reaches the point that it no longer requires engagement of the local facility (e.g., all subsequent follow-up of subjects will be performed by the PI from another facility):

- The PI will notify the LSIs when the study reaches the point at which it no longer requires engagement of the local facility.
- The LSIs will submit Form 117b Local Site Project Participation Closure Report to the PI, who will submit the signed form to the VA Central IRB.
- The LSI will notify their respective local site Facility Director and R&D Committee that their facility will no longer be engaged in the research.

## DATA ANALYSIS PLAN

### Primary aim: Anxiety and Quality of Life differ as a function of bCBT for anxiety vs. EUC

All analyses will be done on an intention-to-treat basis, and participants will be analyzed in the group to which they were randomized. We will first determine whether participants randomized to the two study arms differed on baseline characteristics, age, race, gender, medical or mental health comorbidities, and anxiety. Chi-square tests will be used for categorical variables and t-test for continuous and ordinal variables.

We will examine the normality of the distributions of both primary outcomes and will consider transformations such as the log or the inverse. Because we are using an unequal randomization (see sample size section), it is especially important to test the assumption about the homogeneity of the variance of the residuals across the levels of the independent variables. For analyses of our primary outcomes, we will test the homogeneity assumption before testing for differences between the bCBT and EUC groups. If the assumption of equal variances is violated, we will use statistical tests such as the approximate t-test, which uses individual sample variances instead of the pooled variance. In addition, we will obtain Satterthwaite's approximation of the degrees of freedom. For the regression models, we will test whether the residual variances are equal and, if necessary, we will fit unequal variance models to obtain better estimates of the standard errors of the difference between groups. We will calculate the absolute differences in outcome measures between baseline and 12-month follow-up and the effect sizes of the bCBT group compared with EUC. We will also examine effect sizes for the bCBT group baseline vs. post-treatment and 8-month follow-up.

To compare changes in anxiety symptoms between the two groups over time, we will use a longitudinal, mixed-model analysis containing terms for the intercept, treatment, time, and interaction between time and treatment. In separate analyses, we will compare changes in quality-of-life between the two groups over time using a similar mixed-model approach. The mixed-model analysis will allow us to nest patients by site. Any baseline characteristics found to be significantly different between bCBT and EUC will be included in the model, *as will any differences in mental health service use*. The four time points (baseline, 4-, 8-, and 12-month) will allow us to assess the immediate impact of treatment and the longer-term retention, improvement, or decay in outcomes. The treatment effect will measure differences between the intervention and control groups at baseline, and the time effect will measure whether there was an overall change over time in the outcome. The term of most interest will be the interaction between time and treatment, which will indicate whether there is a difference over time between the two groups. The use of the random-coefficient model will allow us to fit a line for each participant using his/her available data, including participants with missing values, and maximize the power to detect differences.

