Eligible participants (those who screen positive for anxiety on the GAD-7) will be sent a consent form and HIPPA medical records release form for review and signatures either by mail or VA-approved encrypted email (e.g.: Azure RMS, MyHealtheVet, DocuSign) according to participant preference. The potential participant will be called within two weeks to discuss the informed consent documents (Appendix 5D, Veteran ICF and Appendix 5L, HIPAA) and to have any questions answered. A full baseline assessment will be scheduled within two weeks of receiving the signed informed consent form and HIPPA form. (Note: No baseline will be completed until the signed study consent and HIPPA form have been returned.) The independent evaluator or RA assigned to complete the baseline will administer assessments to confirm the presence of anxiety (Appendix 8A, GAD-7) and non-presence of cognitive impairment (see Appendix 6A, Cognitive Screen), of bipolar and psychotic disorders and substance use (Appendix 6B, MINI), and of alcohol use (Appendix 6C, AUDIT-C). The independent evaluator or RA will also administer the Diversity Supplement assessments (Appendix 6E, Diversity Supplement) to evaluate whether sociocultural factors are associated with the severity and type of anxiety symptoms among Veterans of different race/ethnicity groups.

Stage IV:

Participants still eligible following the baseline assessment will be randomized to the direct referral or EUC groups.

Provider Participants:

Provider participants will be recruited from the Houston, San Antonio, and New Orleans sites. PCMHI clinic leads have endorsed the project and national union representatives will be informed of the study prior to initiation of the project. PCMHI staffing levels at the three facilities are robust - Houston has 12 psychologists and 4 social workers; San Antonio has 15 psychologists, 7 social workers, and 2 master's level counselors. New Orleans has 2 psychologists, and 2 social workers and is in the process of expanding their PCMHI program. In addition, PCMHI social work and psychology interns and fellows are eligible to participate. Target recruitment of 32 providers is conservative given staffing levels, new mental health hiring initiatives, trainee participation, and staff turnover.

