Analyses will use data from the mixed-method formative evaluation described above. Qualitative pre-implementation data will be analyzed using rapid qualitative analysis, a systematic and rigorous process, to provide data in real-time to tailor the intervention, and identify contextual barriers prior to rollout^{38,39,40}. Implementation and post-implementation interviews with providers and Veterans will be analyzed using directed content analysis⁴¹ consisting of deductive (a priori) codes from the RE-AIM QuEST framework. Inductive (a posteriori) codes that emerge from providers' and Veterans' experiences with the intervention and VVC-H delivery will also be identified. We will utilize Atlas.ti software to facilitate analysis and management of qualitative data. Quantitative data will be collected and analyzed as descriptive data.

Sample Size and Power Calculations

Primary Aim: To determine whether anxiety symptoms (GAD-7) and quality of life (SF-12) differ as a function of the intervention (bCBT for anxiety vs. EUC) at 4-, 8-, and 12-month follow-ups. A three-step sample-size calculation indicates that 225 anxiety patients will need to be randomized to draw conclusions regarding the primary hypothesis that bCBT will be superior to EUC at 4-, 8, and 12-month assessments.

Step 1: Power to detect GAD-7 differences. A sample size of 138 anxiety patients is needed to detect an effect size = 0.38 for the differences between bCBT and EUC GAD-7 outcomes using a two-sided t-test with 80% power at the .05 significance level, adjusted for repeated measures³⁷. The formula for the sample size, adjusting for repeated measures, is

$$N = \frac{2 * (Z_{(1-\alpha/2)} + Z_{(1-\beta)})^2 [1 + (T - 1) \rho]}{d^2 T}, \text{ where } N \text{ is the sample size per group, } Z_{(1-\alpha/2)} \text{ and}$$

$Z_{(1-\beta)}$ are the $(1-\alpha/2)$ and $(1-\beta)$ percentiles of the normal distribution, T is the number of follow-up measures, ρ is the correlation coefficient of the repeated measurements, and d is the effect size⁴². Solving this with $T = \text{three follow-up measurements after baseline}$, $d = 0.38$, and $\rho = .7$ yields a sample size per group of 69, and total sample $N^t = 138$.

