Step 3: Provider Inflation Factor. The bCBT sample size was then inflated to account for the intraclass correlation due to clustering of patients within providers⁴³. We also will adjust the sample sizes for both the bCBT and EUC groups to account for attrition. Because only participants receiving bCBT are assigned to a provider, we first determined the average number of bCBT patients per provider (87 bCBT patients/25 providers = 3.5 patients per provider). To account for clustering in the bCBT group, the number of bCBT patients is inflated by the factor $[1 + (\bar{m} - 1) c]$, where \bar{m} is the average number of bCBT patients per provider and c is the correlation among patients seen by the same provider. Based on the sample size of 87 bCBT patients and an assumed correlation among patients of .10⁴³, our inflation factor is 1.25 ($87 \times 1.25 = 109$). Finally, to account for attrition, we assumed an attrition rate at 1 year of 25% ($109 \times (1/0.75) = 145$) gives 145 bCBT patients. A similar clustering inflation factor was not used for the EUC group, as no providers are assigned. Attrition rate of 25% was assigned to the EUC group ($58 \times (1/0.75) = 78$), rounded to 80 for randomization. The final number of randomized patients equates to 225 (145 bCBT and 80 EUC).

Secondary Aims:

Prediction of bCBT response and VVC-H use (bCBT group only). To assess predictors of bCBT response and VVC-H use, at least 10 events per variable in the logistic-regression models are needed to have unbiased estimates of the sample variance of the regression coefficients⁴⁴. No sample-size calculations were conducted for secondary aim, but SAS[®] proc power (version 9.4)⁴⁵ indicated a sample of 145 is adequate for 80% power to test odds ratio of 2.5, and conservative estimates for sample size and assumptions necessary to run the analyses suggest the project will be appropriately powered for 10 variables⁴⁶. Secondary analyses will include 8 variables for aim 2A (bCBT response; model #1) and 8 variables for aim 2B (VVC-H prediction; model #2).

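### The bCBT arm is sized for clustering of patients within providers, but the primary model has no provider term; Step 3 also takes its cluster size from the count before inflation

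*SAP*

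**What the plan says.** **Sizing.** Protocol 5.6, Step 3: "The bCBT sample size was then inflated to account for the intraclass correlation due to clustering of patients within providers". The assumed correlation is .10. EUC gets no such inflation because its patients have no assigned provider. The cluster size is "87 bCBT patients/25 providers = 3.5 patients per provider", which gives a factor of 1.25. That takes 87 bCBT patients to 109, and 25% attrition takes 109 to 145 randomised. With 80 EUC the total is 225.

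**Analysis.** The SAP (Primary aim) and Protocol 5.6 describe the same mixed model: intercept, treatment, time, time-by-treatment, and a random-coefficient line for each participant. Baseline is one of four time points, and the interaction is the term of most interest. The only grouping above the patient is site: "The mixed-model analysis will allow us to nest patients by site". No provider effect is named.

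**Provider count.** Protocol 5.1 (bCBT Providers) and Step 3 use 25. Protocol 5.2 says: "Target recruitment of 32 providers is conservative given staffing levels".

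**The concern.** Clustering in one arm only is a partially nested design. The protocol judged the correlation large enough to add 22 evaluable bCBT patients (109 − 87), yet the model treats bCBT patients within a site as independent. If the correlation is real, the modelled standard error of the arm comparison is too small, intervals are too narrow, and the two-sided test rejects more often than 5%.

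Nothing else in the plan supplies the missing level. A site term cannot absorb variation between providers within a site that exists in one arm only. The unequal-variance option lets the arms differ in variance but leaves bCBT patients uncorrelated. The hierarchical models under Missing Data (Protocol 5.6) are sensitivity work and name no provider level.

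Step 3 has a second, smaller problem. It computes caseload from 87 patients, although the same step ends with 109 evaluable and 145 randomised in that arm.

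**Working it through.** **1. Reproduce Step 3.**
- Factor = 1 + (m − 1) × .10, with m = 87/25 = 3.48 (rounded to 3.5): 1.25.
- 87 × 1.25 = 108.75, so 109. 109/0.75 = 145.3 (stated 145). 58/0.75 = 77.3, so 78, rounded by the protocol to 80. Total 225.
- Step 3 therefore reproduces from its own inputs.

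**2. Standard error when provider is left out.** Inputs: correlation .10 and 25% attrition from Step 3. Analysed: 145 × 0.75 ≈ 109 bCBT and 80 × 0.75 = 60 EUC. Caseloads are taken as equal.
- DE = 1 + (m − 1) × ICC
- SE ratio (true/modelled) = √[(1/n_EUC + DE/n_bCBT) / (1/n_EUC + 1/n_bCBT)]
- Type I error = 2 × [1 − Φ(1.96 / SE ratio)]

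For 25 providers, m = 109/25 = 4.36 and DE = 1.336. The variance ratio is (0.016667 + 0.012257)/(0.016667 + 0.009174) = 1.119, so the SE ratio is 1.058 and type I error is 6.4%.

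| Providers | bCBT / EUC analysed | m | ICC | DE | SE ratio | Type I error |
|---|---|---|---|---|---|---|
| 25 | 109 / 60 | 4.36 | .10 | 1.336 | 1.058 | 6.4% |
| 32 | 109 / 60 | 3.41 | .10 | 1.241 | 1.042 | 6.0% |
| 25 | 145 / 80 (no attrition) | 5.8 | .10 | 1.48 | 1.082 | 7.0% |
| 25 | 109 / 60 | 4.36 | .02 | 1.067 | 1.012 | 5.3% |
| 25 | 109 / 60 | 4.36 | .05 | 1.168 | 1.029 | 5.7% |
| 25 | 109 / 60 | 4.36 | .15 | 1.504 | 1.086 | 7.1% |

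The ICC values other than .10 are an assumed range.

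As a cross-check, 20,000 simulated trials used one change score per patient, providers spread over three sites, site in the model and provider ignored. At ICC .10 with 109 and 60 analysed, rejection was 6.6% with 25 providers and 5.8% with 32. At ICC 0 with 25 providers it was 5.3%.

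**3. Cluster size in Step 3.**
- 25 providers: factor 1.336 on the analysed count. 109/1.336 = 81.6 independent patients, against the 87 required.
- 32 providers: factor 1.241. 109/1.241 = 87.9, so 1.25 is adequate.

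The power cost uses Step 1's own terms: "A sample size of 138 anxiety patients is needed to detect an effect size = 0.38", a "two-sided t-test with 80% power at the .05 significance level, adjusted for repeated measures", T = 3 and ρ = .7. The variance multiplier is (1 + 2 × .7)/3 = 0.8, and power = Φ(0.38/√[0.8 × (1/60 + DE/109)] − 1.96).
- DE = 1.25: 71.7%
- DE = 1.336: 70.5%

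The loss is about 1 point. Both values lie below 80% for a separate reason. Step 1 says that it "yields a sample size per group of 69", but its printed formula with two-sided .05 gives 2 × (1.960 + 0.842)² × 2.4/(0.38² × 3) = 87 per group; one-sided .05 gives 68.5, hence 69.

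**4. Which provider effect the tested term needs.** A provider intercept shifts all of a patient's time points equally, so with balanced data it drops out of that patient's slope. If providers differ in how fast their patients improve, an intercept alone leaves the time-by-treatment standard error uncorrected. A generalised-least-squares check with illustrative variance components showed this pattern: the ratio of true to modelled variance was 1.076 with no provider term, still 1.076 with a provider intercept, and 1.00 once a provider slope was added.

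**The case against.** Several points on the other side stand.

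- **The effect is modest.** Only one arm is clustered and clusters are small. The documents do not say that .10 applies to the time-by-treatment contrast; at .02 the inflation is negligible.
- **The cluster-size point depends on the provider count.** With 32 providers it disappears on the analysed count, leaving a 25-versus-32 discrepancy.
- **Part of the remedy is already there.** The plan allows unequal-variance models and, for the t-test, Satterthwaite degrees of freedom.

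A reader might also infer more than the documents support:

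- *That the error favours bCBT.* The excess is two-sided and symmetric under the null. At 6.4%, each direction has about 3.2% instead of 2.5%.
- *That the bCBT arm is worth only 74 patients.* That is 109/1.48, which divides analysed patients by a factor built on randomised ones (145/25 = 5.8). If all 145 were analysed, 145/1.48 = 98, above the 87 required. Nor would every provider treat 5.8 patients: Protocol 5.3 and 5.5 plan interviews with bCBT Veterans who attended no sessions.
- *That uneven caseloads push the error much higher.* Unevenness would raise it, but the documents give no caseload distribution from which to say by how much.
- *That three sites are too few for a random effect.* The plan does not say that site is random.

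**Conclusion.** The sizing and the primary analysis rest on different assumptions about clustering, and the analysis omits the level that the sizing paid for. At the protocol's own ICC and on analysed counts, the true standard error is about 4% (32 providers) to 6% (25 providers) above the modelled one, and two-sided type I error is about 6.0% to 6.4%. It reaches about 7.0% only with 25 providers and no attrition. At 4.36 patients per provider it runs from 5.3% to 7.1% over the assumed ICC range of .02 to .15. These figures assume equal caseloads and that the ICC applies to the tested contrast.

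The Step 3 cluster size is too small for the 25 providers it uses (factor 1.34 against 1.25, about 1 point of power) but not for 32. The omission should be corrected because it touches the validity of the primary test; its size does not put the trial's conclusions at serious risk.

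**What to change.** **Analysis, in both Protocol 5.6 and the SAP, before outcomes are compared by arm.** Pre-specify a partially nested mixed model:
- provider random effects for bCBT patients only, with a provider-by-time (slope) effect as well as an intercept, so that the time-by-treatment test is corrected;
- EUC patients as singletons;
- a stated rule for bCBT patients with no sessions, for example the provider to whom they were referred;
- arm-specific residual variance;
- Kenward-Roger or Satterthwaite degrees of freedom.

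**Sizing.** Reconcile 25 with 32 providers, recompute Step 3 from the analysed bCBT caseload, and restate the power. A loss of about 1 point does not call for enrolling more patients.

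**Cost.** No new data collection: bCBT referrals go to individual study-consented providers and sessions are recorded in templated notes (Protocol 5.1). The price is slightly wider intervals and a little more modelling work.

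### The plan does not say how imbalanced baseline characteristics enter the model; as main effects they leave the time-by-treatment term almost unadjusted

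*SAP*

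**What the plan says.** The primary-aim text is the same in the SAP and in Protocol section 5.6. It first tests whether the arms "differed on baseline characteristics, age, race, gender, medical or mental health comorbidities, and anxiety". It then specifies a "longitudinal, mixed-model analysis containing terms for the intercept, treatment, time, and interaction between time and treatment" for GAD-7, and a similar model for quality of life. Baseline is an outcome row alongside months 4, 8 and 12.

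The terms are given roles: "The treatment effect will measure differences between the intervention and control groups at baseline", and "The term of most interest will be the interaction between time and treatment". The rule for imbalance is "Any baseline characteristics found to be significantly different between bCBT and EUC will be included in the model". Nothing says whether such a characteristic enters as a main effect or also interacts with time.

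The random-coefficient model is meant to "fit a line for each participant using his/her available data, including participants with missing values". Step 3 of the sample-size section in Protocol 5.6 allows for 25% attrition at one year.

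**The concern.** A person-level covariate entered as a main effect shifts all four of a participant's scores by the same amount. The time-by-treatment term compares change between arms, and a constant shift drops out of change. The adjustment therefore falls on the treatment main effect, which the plan defines as the baseline difference, and not on the term that decides the trial.

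This matters when the imbalanced factor predicts how much participants change. Baseline anxiety is on the list of tested variables and is an obvious candidate: entry requires a GAD-7 of 10 or more (Protocol 5.4), so regression to the mean is expected. If it is the variable that differs, GAD-7 at baseline becomes both an outcome row and a covariate, a case the plan does not address. The choice of covariates by significance test is a separate matter. A well-chosen, prespecified covariate entered as a main effect would have the same limitation.

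**Working it through.** The documents give no figure for this adjustment, so there is none to reproduce.

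**Algebra.** Let A be arm, X a baseline covariate and t time. With X as a main effect,

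Y(t) = b0 + b1·A + b2·t + b3·A·t + g·X + u0 + u1·t + e(t).

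Subtract the baseline row:

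Y(t) − Y(0) = b2·t + b3·A·t + u1·t + e(t) − e(0).

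The term g·X has gone. If X also predicts change, the true model contains h·X·t. The arm difference in mean change is then (b3 + h·δ)·t, where δ is the arm difference in mean X. A main effect of X cannot remove h·δ; an X-by-time term can.

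**Numerical check.** From Protocol 5.6: 145 bCBT, 80 EUC, four visits, 25% attrition. Assumed, because the documents give no values: imbalance 0.4 SD; covariate effect 2 points per SD on level and 0 or 0.5 per visit on slope; intercept variance 9; slope variance 0.8; residual SD 2.5; true time-by-treatment slope −0.5. The table shows mean REML estimates of that slope over 40 simulated trials per row.

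| Scenario | No covariate | Main effect | Covariate-by-time |
|---|---|---|---|
| Complete data, X affects level only | −0.445 | −0.445 | −0.450 |
| Complete data, X also affects slope | −0.245 | −0.245 | −0.450 |
| 25% random dropout, level only | −0.452 | −0.455 | −0.465 |
| 25% random dropout, also slope | −0.250 | −0.254 | −0.465 |
| 30% dropout tied to X differently by arm, level only | −0.582 | −0.466 | −0.468 |
| Same dropout, also slope | −0.554 | −0.454 | −0.468 |

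- In row 1 the Monte Carlo error of a mean is 0.196/√40 = 0.031, so −0.445 lies (0.5 − 0.445)/0.031 = 1.8 errors from −0.5. The useful comparison is across columns.
- Complete data: the main effect changes nothing, and the standard error is 0.196 with or without it (row 1). Generalised least squares with known covariance gave differences below 1e-12, for linear and categorical time, with and without a site variance. Only the treatment term moved, from 0.69 to −0.11.
- The bias in row 2 is as the algebra predicts: h·δ = 0.5 × 0.4 = 0.20, against −0.245 − (−0.445) = 0.200 observed. The main effect removes none of it.
- Random dropout: the mean absolute shift was 0.016 in row 3 (standard error 0.22) and 0.022 in row 4 (standard error 0.235). With known covariance the mean shift was about 0.06 to 0.08 standard errors, the largest 0.26.
- Arm-specific dropout tied to X: in row 5 the main effect moved the estimate by 0.116, or 0.116/0.224 = 0.52 standard errors, towards the truth. The last row mixes dropout bias with imbalance bias and should not be read as either alone.

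**Size in this trial.** Smallest imbalance reaching two-sided p < .05: 1.96 × √(1/145 + 1/80) = 0.273 SD. Take the repeated-measures correlation of .7 (Protocol 5.6, Step 1) to hold between baseline and month 12, with equal SDs. The SD of change is then √(2 × (1 − 0.7)) = 0.775 outcome SD. With r the correlation of the covariate with 12-month change, the bias left in is r × 0.273 × 0.775:

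- r = .2: 0.042 SD, 11% of 0.38
- r = .3: 0.063 SD, 17%
- r = .4: 0.085 SD, 22%

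The range for r is assumed. For the baseline score itself, the same correlation of .7 implies |r| = √((1 − 0.7)/2) = 0.39, and a bias of (1 − 0.7) × 0.273 = 0.082 SD, near the top of the range.

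**The case against.** The strongest reply is that the main effect is a reading, not the plan's text. That stands: the form is unspecified. But the covariate is added to a list of named terms in which only treatment interacts with time, so a main effect is the natural reading. If another form was meant, the sentence needs changing anyway.

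A reader might infer that the rule does nothing, or that a covariate cannot move the interaction. The documents do not support this. It is exact only with complete data, and the plan expects 25% attrition and keeps incomplete records. Under random dropout the term moves a little in single trials, and under arm-specific dropout tied to the covariate a main effect removes real bias. That is correction of missing-data bias, however, and not of the baseline imbalance that triggers the rule.

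A reader might also infer that the key test has no other protection against imbalance. That is wrong too. The treatment term absorbs the baseline difference, so a factor with a constant effect on level leaves nothing to correct in the interaction with complete data.

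Finally, randomisation keeps the estimate unbiased over all possible trials, and each test triggers the rule by chance about 5% of the time. The bias is therefore conditional and occasional, and its size rests on an assumed correlation. All of this stands and limits the weight of the point. Nor do the documents say how results will be labelled, so misreporting as adjusted should not be presumed.

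**Conclusion.** The point holds as a gap in how the adjustment is specified. On the natural reading, the planned response to baseline imbalance barely acts on the term that decides both primary outcomes when the imbalanced factor predicts change. The exceptions are small shifts under random dropout and a material one when dropout depends on the covariate differently by arm.

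The conditional bias left in is about 0.04 to 0.08 SD at the triggering imbalance, or 11 to 22% of the planned effect of 0.38, and it grows in proportion to the imbalance. This rests on the protocol's correlation of .7 applying from baseline to month 12, equal SDs across visits, an assumed correlation of .2 to .4 between covariate and change, and a significant imbalance having occurred. It is modest and does not invalidate the design, but it should be settled before the analysis.

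**What to change.** Amend the primary-aim text in both the SAP and Protocol 5.6 in one of two ways.

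1. Take baseline out of the outcome rows. Model the 4-, 8- and 12-month scores on treatment, visit, treatment-by-visit, the baseline score of that outcome (GAD-7 or SF-12V) and the baseline covariates. The sentences defining the treatment term and the term of most interest must then change, because the effect of interest becomes the treatment contrast at the follow-up visits.
2. Keep baseline as an outcome row, enter each baseline covariate together with its interaction with time, and state that the baseline outcome score is not also entered as a covariate.

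The first is preferable because it also handles imbalance in the baseline score itself, which the second leaves in the change comparison. Naming the covariates in advance would avoid adding data-dependent terms to the primary model under either option.

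The cost is a short amendment and no new data. The second option uses 1 degree of freedom per covariate with linear time, or 3 with visit categories. In a check at 145:80, covariate-by-time terms raised the standard error of the interaction from 0.199 to 0.202. Under the first option, a participant with no follow-up score contributes no outcome row.
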